see which treatment options have offered the best outcomes. Closer monitoring of patients beyond this on a day-to-day basis provides the ability to change treatment pathways or provide interventions in a preventative manner, identifying potential adverse events or outcomes before the point of no return. The aim of this study is therefore to build a digital patient profile which will help to support the study of SCD's natural history, produce risk stratifications, predict long-term impacts, and create a correlation matrix of metrics signalling, for example, a potential crisis or the early stages of progression to renal failure, flagging issues earlier in the cycle for faster interventions, or even raising the alarm before a crisis is triggered. Patients will have full visibility of their data and the resulting insights to manage their own care more effectively and pre-emptively, with support from clinicians through earlier detection of adverse events.

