The main objective of this project is to establish a digital patient profile to identify and monitor for the key risk factors or triggers around SCD pathologies, such as VOC and organ damage, as well as the best treatment options for these patients. Furthermore, the resulting unified platform will help to collate the necessary information needed to empower patients in managing their own care, and access specialist clinician advice as and when they need it.

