7.2 Patient Withdrawal

Patients may voluntarily withdraw from the study at any time, as protected by GDPR, or be dropped from it at the discretion of the responsible clinician (investigator) at the NHS Trust. Patients may be withdrawn from the study if any of the following occur:

Patient or parent withdrew consent

Lost to follow-up

Death

Administrative problems

For patients who are lost to follow-up, the investigator will show 'due diligence' by documenting steps taken to contact the patient, such as dates of telephone calls, and mailings.

8. Statistical Analyses

An initial high-level investigation using descriptive analysis will be conducted across all variables in order to identify key trends and insights, from which further correlations and statistical significance will be tested. This will predominantly be performed using IBM SPSS Statistics 24 and Microsoft Excel, collected data analysed for outliers through Boxplot and Q-Q Plots, for normal distribution using Shapiro-Wilks testing, and for homogeneity of variance using Levene's testing. Due to the exploratory nature of the study, hierarchical stepwise regression of the outlined data points (Section 4.2 & 4.3) will be conducted, and any outliers detected through assumption testing will not be immediately excluded from analyses, instead further investigated to identify any clinically significant causes. For data that do not violate these assumptions, either independent t-tests (for experiments with two experimental groups) or one-way ANOVA (for experimental groups of 3 or more) will be performed, with Bonferroni post-hoc testing. Those that do violate these assumptions will undergo non-parametric Kruskal-Wallis testing. Each analysis will be based upon demographic variables, such as age and gender, correlated against genetic and clinical variables including hospital admissions, comorbidities, genotype, phenotype, and wearables collected data (Section 4.3). Those with p-values below 0.05 will be considered as statistically significant and undergo further study.

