An additional focus for the study regards data collected over extended periods of time and the progression of the disease state over this period, therefore requiring the inclusion of two independent variables. For such data, this will require Mauchly's test for sphericity in addition to Shapiro-Wilks testing for normal distribution. These data will then be tested for statistical significance using a two-way repeated measures ANOVA with a Bonferroni adjustment. Each step of the analytical output will be reported alongside changes in variance and F change, and collinearity of the independent variables will be investigated within the regression model.

This statistical analysis will in part feed into and be supported by the data platform's advanced AI and ML algorithms. However, the primary purpose of the AI technology will revolve around the predictive element of this study, highlighting potential outcomes and suggestions for optimal treatment pathways based upon the statistical analysis conducted, and key trends or associations identified.

9. Administrative Procedures

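### Section 8 names least-squares regression and rank or mean-based group tests for everything, though some of the variables it must analyse are categories or counts

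*Protocol*

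**What the plan says.** Section 8 states its methods by name. The regression is given as "hierarchical stepwise regression of the outlined data points (Section 4.2 & 4.3) will be conducted", and its output is specified: "Each step of the analytical output will be reported alongside changes in variance and F change". No dependent variable is named.

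For group comparisons, where normality and equal variance hold, "either independent t-tests (for experiments with two experimental groups) or one-way ANOVA (for experimental groups of 3 or more) will be performed". Where they do not, "Those that do violate these assumptions will undergo non-parametric Kruskal-Wallis testing". Data followed over time go to a two-way repeated measures ANOVA. No logistic, count, time-to-event, chi-square or Fisher method appears.

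The variables to be set against age, gender and other demographics are "genetic and clinical variables including hospital admissions, comorbidities, genotype, phenotype, and wearables collected data". Section 3 gives the main objective as a profile to "identify and monitor for the key risk factors or triggers around SCD pathologies, such as VOC and organ damage", and Section 2.1 wants the profile to "produce risk stratifications, predict long-term impacts". Section 8 also sends any result with p below 0.05 forward for further study, and says that the platform's treatment-pathway suggestions will rest on this analysis.

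**The concern.** Change in explained variance and F change belong to a linear model fitted by least squares. Maximum-likelihood logistic and count models are compared by change in deviance instead. Section 8 therefore settles on one regression family for all outcomes.

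Many of the Section 4.3 measurements suit that family. Several variables named in Section 8 do not:

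- Comorbidities are present or absent.
- Genotype is unordered: Section 1.1 describes SS, or S with C or with beta thalassaemia.
- Phenotype is likely to be a category too.
- Hospital admissions are counts.
- Crises and organ damage become yes/no or counts if scored as occurrence.

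Two things are at stake. Fitted risks for a yes/no outcome may be impossible values or wrong at the extremes, which matters for risk stratification. And for an unordered outcome, a result may pass or fail the 0.05 threshold because of how the categories happen to be numbered.

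**Working it through.** **Inputs.** From the protocol: N = 300 (Section 4.1), significance at 0.05 (Section 8) and the named methods. The 300 is 2% of the upper population figure (0.02 × 15,000 = 300; 0.02 × 12,500 = 250) and is used here only as a sample size. The protocol gives no event rate, effect size or genotype distribution, so those below are assumptions.

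**Part 1: least squares on a yes/no outcome.** Take one standard-normal predictor z, event rate π and odds ratio OR per SD.

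- True risk: p(z) = 1 / (1 + exp(−(a + bz))), with b = ln(OR) and a chosen so that the mean risk is π.
- Least-squares line: π + s·z, with s = E[z·p(z)].
- Share of fitted risks below 0: Φ(−π/s). Share above 1: 1 − Φ((1 − π)/s).

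Worked case, π = 0.10 and OR = 3: b = 1.099, a = −2.633, s = 0.0880. At +2 SD the line gives 0.10 + 2 × 0.0880 = 0.276. The true risk is 1 / (1 + exp(0.436)) = 0.393. The share below zero is Φ(−0.10/0.0880) = Φ(−1.136) = 12.8%.

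| π | OR | True at +2 SD | Line at +2 SD | Below 0 | Above 1 |
|---|---|---|---|---|---|
| 0.10 | 2 | 0.270 | 0.219 | 4.7% | 0 |
| 0.10 | 3 | 0.393 | 0.276 | 12.8% | 0 |
| 0.20 | 3 | 0.622 | 0.497 | 8.9% | 0 |
| 0.50 | 3 | 0.900 | 0.941 | 1.2% | 1.2% |
| 0.70 | 3 | 0.963 | 1.078 | 0.0% | 5.6% |

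The line is too low at the top for uncommon outcomes and too high for common ones. In 2,000 simulated data sets of 300 at π = 0.10 and OR = 3, logistic regression averaged 0.400 at +2 SD against a true 0.393; least squares averaged 0.276.

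If the outcome were a crisis on a given day, at an assumed 1 to 6 per year and OR 2 or 3, the line is negative on 7% to 18% of days. The ratio of true to fitted risk is 0.79 to 0.94 at +1 SD, 1.3 to 1.5 at +2 SD and 1.9 to 3.4 at +3 SD.

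**Part 2: an unordered outcome with three levels.** Assumed table of 300 patients, three groups by outcome levels A, B, C: (110, 40, 40), (40, 30, 10), (12, 12, 6).

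- Pearson chi-square = 11.63 on 4 df, p = exp(−5.813) × (1 + 5.813) = 0.020, whatever the labels.
- Kruskal-Wallis ranks the code numbers. It has 2 df, so p = exp(−H/2).

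| Level coded in the middle | H | Kruskal-Wallis p |
|---|---|---|
| B | 1.887 | 0.39 |
| C | 6.780 | 0.034 |
| A | 8.986 | 0.011 |

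The data are the same and only the numbering differs. A second assumed table (three groups, four genotype levels, 300 patients; chi-square p = 0.018) was run over all 24 codings. Kruskal-Wallis p ran from 0.004 to 0.132, with 16 of 24 below 0.05. ANOVA p ran from 0.004 to 0.594, with 12 of 24 below 0.05. With genotype entered as one numeric code in a regression on a simulated continuous outcome, p ran from 0.00006 to 0.81.

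**Part 3: where the named tests are sound.**

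- Genotype as the grouping factor in Kruskal-Wallis gives one p-value for every ordering.
- For a yes/no outcome, Kruskal-Wallis equals Pearson chi-square × (N − 1)/N. In a 300-patient example H = 7.448 both ways, and p = 0.0241 against 0.0238 for chi-square itself.
- The single-predictor least-squares F test on a 5% or 10% yes/no outcome kept its type I error at 0.050 (20,000 simulations, n = 300).

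**The case against.** The strongest reply is that Section 8 describes an exploratory search for associations, not a risk model. It names no dependent variable, most Section 4.3 data points are measured quantities, and the predictive work is assigned to the AI component. A test of association by least squares is not badly calibrated in the simple case (Part 3). Choosing a model by variable type is also commonly left to a statistical analysis plan.

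Much of this stands. It limits the point in four places where a reader might infer more:

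- **That risk is understated where it is highest.** This holds for uncommon outcomes but reverses for common ones, and the protocol gives no event rate. Even in the daily-crisis illustration, the large ratios occur only at +3 SD and the line slightly overstates risk at +1 SD. No daily-risk model is stated anywhere in the protocol.
- **That Kruskal-Wallis is the fallback for the regression.** In Section 8 it follows the sentence on t-tests and ANOVA and replaces those group comparisons.
- **That Kruskal-Wallis is wrong for all categorical data.** It is valid for two-level outcomes and with genotype as the grouping factor.
- **That crises and organ damage are yes/no.** The protocol sets no scale for them. Yes/no is an inference from the aim of early warning; they may equally be counts or recurrent events.

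The reply does not remove the point. The protocol has not left the method open: it fixes F change and variance, and names one fallback. Section 8 itself lists comorbidities, genotype, phenotype and admissions for analysis. It also says that the treatment suggestions will build on this analysis, though not that fitted linear risks will be used as alerts.

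**Conclusion.** The concern holds as a mismatch between the methods Section 8 fixes and the scale of some variables it must analyse. For yes/no outcomes, least-squares risks are distorted at the extremes and can leave the 0 to 1 range: up to 12.8% of fitted values below 0, or 5.6% above 1, in the tabulated settings. The direction is not established, because it depends on event rates that the protocol does not state. For unordered outcomes with three or more levels, ANOVA and Kruskal-Wallis p-values depend on code numbers and can cross 0.05 on that account alone (0.011 to 0.39 in the three-level example). Counts such as admissions also have no suitable model named. All event rates, odds ratios and tables are assumptions that show the mechanism; they are not estimates for this cohort. The point should be corrected before analysis. It does not affect recruitment or data collection.

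**What to change.** In Section 8, state the scale of each outcome and let it determine the method, keeping the planned hierarchical blocks:

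- **Yes/no outcomes** (a comorbidity, or a crisis or organ complication scored as occurrence): logistic regression, clustered by patient where measurements repeat.
- **Counts** (admissions, and crises if counted): a count or recurrent-event model.
- **Pairs of unordered variables**: chi-square or Fisher tests.
- **Genotype as a predictor**: indicator variables, not one numeric code.
- **Reporting for these outcomes**: change in deviance by likelihood ratio, or a Wald test for clustered models, with odds or rate ratios, in place of variance and F change.
- **Continuous or ordered outcomes**: keep least squares, ANOVA and Kruskal-Wallis.

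The cost is a revision of Section 8, a little more analysis work, and a written scale for each outcome, including what counts as a crisis if crises are modelled. No new data are needed.

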9.1 Ethical Compliance

The project protocol will be reviewed and approved by an NHS Research Ethics Committee. The proposed patient information sheet and informed consent form will be in accordance with the guidelines from the NHS National Research Ethics Service.

As per the European Union's GDPR, data generated by any wearable device, regardless of its approval as a medical device, will require full consent from each patient with clearly defined purposes for use, consent for which can be withdrawn by patients at any time.

9.2 Research and Development

The London North West University Healthcare NHS Trust and Barts Health NHS Trust's Research and Development Departments will also register the study protocol in accordance with their research governance guidelines.

9.3 Involvement of Service Users

Service users would be an integral part of the project. They would be involved in the project set up, preparation of materials, and project meetings. Service users would be identified through the Sickle Cell Society, London North West University Healthcare NHS Trust and Barts Health NHS Trust, as well as other NHS treatment centres as the study expands, in accordance with the guidelines of Involve (invo.org.uk).

9.4 Data Security

Data security will be ensured through the implementation of strict IT security controls, in-line with those of peers and adopting best practices in areas such as encryption, data anonymisation or pseudonymisation, and identity and access management. This is based on up-to-date appraisals of their security gaps in personal data. Remote access into the trust environment will occur with explicit authorisation from named leads within the trust's business intelligence team via VPN/Citrix/TeamViewer or other remote connectivity. Data from NHS trusts and from the pilot study wearable devices will be collected and stored within a highly secure cloud foundation managed by Microsoft, the infrastructure and cyber security provided by Azure's multi-layered, built-in security controls and unique threat intelligence to identify and protect this data against any risks.

